As with any study in which subjects are asked to take a medication, compliance is an issue. Once a week, the number of pills returned in the blister pack will be subtracted from the number of units dispensed to obtain a measure of the amount of medication consumed by the subject throughout the week. To improve tolerance and thereby compliance, baclofen will be introduced slowly to minimize the possibility of undesirable side effects, such as sedation. The study physician or the nurses under the physician's supervision will monitor administration of study medication. See Dispensation Schedule (below). The key describes how the medication will be administered. P = placebo, O = 10 mg baclofen, X = 20 mg baclofen. There are two pills in every blister. These are packaged by IDS to accommodate the titration and taper. Once the full dose is reached (Day 4) and if a subject experiences discomfort or adverse events that may be related to the medication the dose will be decreased until symptoms remit. This will be accomplished by consultation with the Medication monitoring team (Study Physician and Nurses), who will determine if the adverse events might be medication-related. The subject will then be instructed to only take one of the two pills within each blister and disregard the other pill. This lower dose may be maintained throughout the study if the subject so desires. In our ten years experience with this medication and our ongoing protocol (CURE Protocol # 813953) we have had a few subjects request a reduction in dose so we are prepared for this possibility.

Baclofen Dosing Schedule

Study Day	8 AM	12 Noon	4 PM	8 PM
Day 1	Placebo	10 mg Baclofen	Placebo	10 mg Baclofen

Day 2	Placebo	10 mg Baclofen	10 mg Baclofen	10 mg Baclofen
Day 3	Placebo	20 mg Baclofen	20 mg Baclofen	20 mg Baclofen
Day 4-7	20 mg Baclofen	20 mg Baclofen	20 mg Baclofen	20 mg Baclofen
Week 2 - 7	20 mg Baclofen	20 mg Baclofen	20 mg Baclofen	20 mg Baclofen
Week 8 Day 1-2	Placebo	20 mg Baclofen	20 mg Baclofen	20 mg Baclofen
Week 8 Day 3-4	Placebo	20 mg Baclofen	Placebo	20 mg Baclofen
Week 8 Day 5-6	Placebo	10 mg Baclofen	Placebo	10 mg Baclofen
Week 8 Day 7	Placebo	Placebo	Placebo	Placebo

2nd MRI session Visit (approximately 2 hours)

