Regardless of whether or not the subject has requested an MRI report, if study personnel determine a subject's MRI images are unusual, those images will be forwarded to the Hospital of University of Pennsylvania for examination by a certified neuroradiologist. The neuroradiologist will inform study personnel of any potential problems. The P.I. and/or other appropriate study staff will meet with the subject to discuss his/her MRI and the neuroradiologist's recommendations, if any. If necessary, the subject will be strongly encouraged to follow up with his/her primary care physician.

Risks associated with Baclofen Administration: Baclofen has been used safely as an anti-spastic for many years, but it can be associated with some sedation or drowsiness (particularly in the early dosing). Its effects are often transient and can be alleviated or eliminated by decreasing the dosage. Effects are seldom severe enough to warrant withdrawal of the medication. Baclofen should not be stopped abruptly after chronic use (the body adjusts to the muscle relaxant effects and abrupt cessation can result in muscle spasm). The most common adverse reactions associated with baclofen are transient drowsiness, daytime sedation, dizziness, weakness, and fatigue. Less common side effects include skin rash and itching, shortness of breath, problems in urinating, constipation or diarrhea, dizziness, headache, nausea, irregular heartbeat or chest pain. Ovarian cysts have been found in about 4% of patients with multiple sclerosis that were treated with baclofen for up to one year. In most cases, these cysts disappeared spontaneously while patients continued to receive the drug. Ovarian cysts are estimated to occur spontaneously in approximately 1% to 5% of the normal female population.

Protection: Good clinical practice will be followed in terms of regularly monitoring patients for any side effects of the medication. Pregnant women or those not using an acceptable form of birth control will be excluded from the study. A physician will meet with the subject to prescribe baclofen and discuss its possible side effects. Subjects will be cautioned not to drive or operate machinery during the first few days, and will be instructed not to combine the use of baclofen with alcohol or other sedating drugs or medications. Subjects will be carefully monitored by the physician throughout the study for both common and uncommon side effects of baclofen.

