Stopping Procedures: If the patient is experiencing discomfort due to side effects, reducing the dose and/or early termination will be recommended. Significant side effects (chest pain, irregular heartbeat) would occasion breaking of the blind, removal from the protocol, and provision of appropriate clinical care as indicated. Baclofen will be

tapered according to a pre-determined, conservative schedule following the cue/fMRI session. Subjects will continue to be monitored by the physician until s/he is weaned off of the medication and is not experiencing any discomfort.

Risks associated with Blood Drawing: There is a slight risk associated with the drawing of blood. Bleeding, bruising (only 1-2% significant enough to last more than 24 hrs) or infection (has not been observed due to appropriate sterilization and proficient phlebotomy techniques of staff) may occur at the site of venipuncture.

Protection: Only experienced medical staff will draw bloods under sterile conditions, minimizing any risk. The amount of blood drawn (55 cc) will not pose a risk. Standard policies for safe handling of blood samples will be followed to protect subjects and staff. All individuals who will be handling blood are required to participate in specialized Biohazard training through the University of Pennsylvania.

Risks associated with Confidentiality: Every attempt will be made by the investigators to maintain all information collected in this study strictly confidential unless a subject says he/she intends to harm himself or another or that he/she has abused a child or an elderly person. However, authorized representatives of the Sponsor(s) (if any), the University of Pennsylvania, as well as the Food and Drug Administration (FDA), will have access to and may copy, both medical records and records from participation in this study. This access is necessary to insure the accuracy of the findings and subject safety and welfare. If any publication or presentations result from this research, subjects will not be identified by name. The data are kept in secure, locked areas and access to these areas is possible only through the investigator or research technician.

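### The stopping rules do not separate leaving study drug from leaving the study, discomfort is handled in two ways, and the taper timing conflicts

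*Combined protocol and SAP*

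**What the plan says.** **Dosing text (Study Procedures, Randomization, above the Baclofen Dosing Schedule).** Once full dose is reached on Day 4, "if a subject experiences discomfort or adverse events that may be related to the medication the dose will be decreased until symptoms remit". The subject then takes one of the two pills in each blister, and "This lower dose may be maintained throughout the study if the subject so desires". On the blisters: "These are packaged by IDS to accommodate the titration and taper". The schedule shows full dose to the end of Week 7 and a step-down only in Week 8.

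**Risk text (Risk/Benefit Assessment, 1. Risks and Protections, Baclofen Administration).** "Its effects are often transient and can be alleviated or eliminated by decreasing the dosage". On the need to stop the drug, it adds: "Effects are seldom severe enough to warrant withdrawal of the medication". It also warns: "Baclofen should not be stopped abruptly after chronic use". Irregular heartbeat and chest pain appear among the less common side effects of baclofen.

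**Stopping Procedures (same section).** There are two tiers. Lower: "If the patient is experiencing discomfort due to side effects, reducing the dose and/or early termination will be recommended". Upper: "Significant side effects (chest pain, irregular heartbeat) would occasion breaking of the blind, removal from the protocol", with clinical care as indicated. The paragraph then says that baclofen is tapered on a preset schedule after the cue/fMRI session, and that a physician monitors the subject until the drug has been withdrawn.

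**Analyses (Study Procedures, 2).** The imaging, behavioral and sample-size text names no analysis population, no method for missing outcomes, and no outcome collection after study drug is stopped.

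**The concern.** Urine cotinine and cigarettes per day after the full 8 weeks are named as post-medication outcomes (Objectives, 3. Secondary Outcome Variables), and Aims 2 and 3 compare randomised arms. If a subject who stops the drug also leaves the study, those outcomes are missing for a reason that may be linked to the drug: the two symptoms that trigger removal are on the protocol's own list of baclofen side effects. A comparison of those who remain could then set tolerant baclofen subjects against a less selected placebo group. Because nothing guides the choice between staying on a lower dose and leaving, two subjects with the same complaint can end up with complete and with missing data.

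The taper is a separate matter of internal consistency. The protocol warns against abrupt stopping, yet its own statements on when the taper happens do not agree, and none gives a schedule for someone who exits early.

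**Working it through.** **1. The two handling rules side by side**

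| Trigger | Dosing text | Stopping Procedures |
|---|---|---|
| Discomfort from side effects | Lower the dose; may continue to study end | Lower the dose and/or early termination; no criterion |
| Chest pain, irregular heartbeat | Not named (general adverse-event wording only) | Unblind, remove from the protocol, give care |

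The first row is a real difference: the trigger is the same and one text adds an exit. The second row is largely graded severity.

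**2. What happens to outcomes after an exit**

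The Table of Measures schedules diary and CO at weekly visits and a urine sample at Week 8. No text says whether subjects taken off the drug keep these visits. The physician monitoring promised in the Stopping Procedures is safety follow-up.

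**3. Possible size of the bias**

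The plan has no figure for removals. Its only sample-size figure concerns the genotype contrast and does not bear on this point.

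Inputs: 100 randomised and 15 expected losses (Accrual); 2:1 allocation (Randomization), so 100 x 2/3 = 67 baclofen and 33 placebo.

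Let f be the fraction lost in an arm and g the leaver-minus-stayer difference in outcome. The shift in the completers-only difference between arms is f_B x g_B - f_P x g_P, in baclofen's favour when positive and leavers smoke more. The documents give no g; a range of 0.25 to 1.0 SD is assumed.

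- Losses split 2:1: 10/67 = 14.9% and 5/33 = 15.2%. With equal g, the shift is (0.149 - 0.152) x g, about -0.002 SD at g = 1: effectively zero.
- Same losses, but baclofen leavers differ from stayers by 0.5 SD more than placebo leavers do: about 0.15 x 0.5 = 0.075 SD.
- A few baclofen removals only (3%, 2 of 67; assumed): 0.03 x 0.25 = 0.0075 SD to 0.03 x 1.0 = 0.03 SD.
- Upper bound, all 15 losses in baclofen: 15/67 = 22.4% against 0%. The shift is 0.224 x 0.25 = 0.056 SD to 0.224 x 1.0 = 0.224 SD.

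**4. Bias or power?**

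The smallest difference detectable with 80% power (two-sample t, two-sided alpha 0.05; the plan does not state sidedness) is 0.602 SD at 67:33, 0.655 SD at 57:28 and 0.631 SD at 52:33. One-sided loss costs no more precision than proportional loss, so the issue is bias. At the upper bound, 0.224/0.631 = 0.36, about a third of the detectable difference.

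**5. Taper timeline**

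- Second and last main-study scan: after 3 weeks (day 21), followed by 5 more weeks of treatment (Study Design, 3. Study Duration). The optional sub-study scan comes after 4 weeks (day 28).
- Tabulated full dose: Day 4 to the end of Week 7 (day 49).
- Tabulated taper: starts on Week 8 Day 1, that is 7 x 7 + 1 = day 50 of 56.

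A taper tied to the scan and a taper starting on day 50 are about four weeks apart. Exits on days 1-49, 49/56 = 87.5% of the treatment period, precede the only tabulated taper.

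**The case against.** The strongest reply has five parts.

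- **Severity grading.** A reader might infer that the same symptom leads to three different actions in three places. It does not. The risk text describes and sets no action, and the upper stopping tier answers different symptoms. What stands is narrower: the dosing text and the lower stopping tier differ on discomfort.
- **No sign of an arm difference.** A reader might infer that baclofen itself causes the loss of outcomes. The rules apply to both arms, the risk text calls withdrawal seldom warranted, and the Background reports no side-effect difference between arms in the investigators' earlier smoking trial. The drowsiness range quoted there (10-63%) does not help, since drowsiness is not the removal trigger. This part stands: treatment-related missingness is a credible risk, not an established fact.
- **Continued follow-up.** A reader might infer that diary, CO and cotinine collection definitely stop. No text says so. Equally, no text says that they continue.
- **The study manual.** Study Monitoring assigns discontinuation procedures to a manual that is not among the documents. It may settle outcome collection, but it cannot remove a disagreement between two sections of the protocol.
- **The taper sentence.** A reader might infer that early leavers are meant to stop without any taper. The Stopping Procedures promise both a taper and monitoring. Read loosely, Week 8 also comes after the scan. That turns the conflict into an ambiguity, but still leaves no schedule for an early exit.

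**Conclusion.** The point holds in limited form, as something that should be changed. Three gaps are visible in the text: two rules for discomfort with no criterion between them; exit wording that does not separate drug from study, with no provision for later or missing outcomes; and taper statements that disagree and give no early-exit schedule.

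The effect on the Week 8 comparison cannot be sized from the documents, because they give no removal rate by arm and do not split the 15 expected losses by arm or reason. The illustration runs from about zero (losses 2:1, equal leaver-stayer gap) to about 0.22 SD (all 15 losses in baclofen, gap of 1 SD). The upper end needs two extreme assumptions together and should not be read as a forecast. The documents do not support a claim that the randomised comparison is already compromised.

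**What to change.** 1. State that leaving study medication, for whatever clinical reason the study physician decides, does not end outcome collection. Unless consent is withdrawn, these subjects keep the existing weekly diary and CO, the Week 8 urine cotinine and the follow-up visit.
2. Analyse these subjects in their assigned arm, and state how outcomes that are still missing are handled. Report drug discontinuations, dose reductions and unblindings by arm. This does not repair the brain contrasts for subjects who miss Scan 2, so report Scan 2 missingness by arm as well.
3. The sponsor and study physician should reconcile the dosing text with the Stopping Procedures on discomfort. They should also reconcile Study Duration, the dosing schedule, the risk text and the Stopping Procedures on taper timing, including early exits. No clinical rule is proposed here.

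Cost: protocol wording and a short analysis paragraph; the visits and measures already exist. There would be some extra visit payments. Self-reports from unblinded subjects are open to bias, so CO and cotinine should carry more weight for them.

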6. SUBJECT COMPENSATION

- \$6 for travel for each scheduled appointment (all visits, even if subject does not pass the consent/screening) ● \$25 for the consenting appointment (Consent Visit)
- \$25 for a DNA sample (Physical Visit)
- \$25 if the physical and psychological evaluations are completed on different.
- \$75 for first scanning session (Scan Day 1 Visit)
- \$25 if subject is double-booked and not scanned. A participant is only eligible to be double-booked once.
- \$100 for second scanning session (Scan Day 2 Visit)
- \$100 for third scanning session (Optional Sub-study Scan Day 3 Visit)
- \$5 for each returned medication card
- \$30 additional compensation of treatment subjects for study completion (Follow up Visit).

Payments will be made with either cash or GreenPhire Clincards. Clincards are reloadable prepaid cards that may be used for in-store purchases (by selecting either the "credit" or "debit" option), online purchases, ATM, and cash advances at a bank. Funds added to the card should be available immediately, however, in some cases it may take 1 business day. If a subject loses their card, it will be replaced at no charge. However, if a subject is repeatedly losing their card, they may incur a small fee to replace it, to be determined by the Comptroller's Office at the University of Pennsylvania whom is monitoring Clincard registration/subject activity.

7. Subject Monitoring

Overview: Subjects will be examined and monitored by the certified nursing staff and physicians at the CSA. Psychological testing will be administered by certified therapists. Subjects will be consented and monitored by trained research technicians. The study will be overseen by the PI who will regularly examine medical and research charts.

All study personnel are required to be familiar with the study protocol. Meetings will be held weekly with the PI and study staff to ensure that all procedures are being followed correctly and that data is collected according to the IRB-approved protocol and HIPAA regulations. Research technicians are trained by the PI with the assistance of an explicit set of written study procedures that must be followed by each subject. Research technicians are required to initial and date each study procedure as it is carried out.

Technician Monitoring of Subject: Subjects will meet with the Research technician at each visit to discuss issues, monitor study progress, collect Daily Diaries, answer any questions the subjects may have, and schedule appointments. Subjects will be called in between weekly appointments by the Research Technician to discuss any potential side effects.

Medical Staff Monitoring of Subject: The study medical doctor reviews all physical examination results to determine whether the subject meets general good health requirements. The nurse will meet with the subjects at Version 14 1/6/2017

all visits to discuss study medication, discuss side effects, review any concomitant medications, collect previous weeks' pill packs and take note of any medical concerns the patient expresses with regard to the medication. The nurse will measure vital signs and go over the Adverse Events sheet with the subject.

8. Data and Safety Monitoring

Who will monitor this study? Check all that apply.

This is a low risk, single-site, Phase II study, involving a medication already FDA approved and marketed for the treatment of other illnesses. The study design is straightforward and familiar to the research staff at the CSA. Therefore, one monitor should be sufficient to complete the monitoring process.

- Principal Investigator
- Sponsor or contract research organization
- NCI sponsored cooperative group
- Cancer Center (if mandated by CTSMRC)
- Medical monitor
- Safety monitoring committee
- Center for the Studies of Addiction Coordinator: A study monitor who is knowledgeable in the protocol, regulations, and university approved procedures for conducting and monitoring clinical investigations will be assigned to monitor the study. The monitor will be selected from one of the Study Coordinators working at the University of Pennsylvania Center for the Studies of Addictions.

Written monitoring procedures for monitoring clinical investigations, proposed by the OHR and previously established at the CSA will be implemented to assure the quality of the study and to assure that each person involved in the monitoring process carries out his or her duties.

The Principal Investigator will maintain a record of the findings, conclusions, and action taken to correct errors noted by the monitor for each visit.

Monitoring Responsibilities (conducted by the Study Coordinator). The monitor, in accordance with local and NIH requirements, should ensure that the study is conducted and documented properly by carrying out the following activities:

- a. Verifying that the investigator has adequate qualification and resources and these remain adequate throughout the study period, and that the staff and facilities, including laboratories and equipment, are adequate to safely and properly conduct the study and these remain adequate throughout the study period.
- b. Verifying that the investigator follows the approved protocol and all approved amendment(s), if any.
- c. Verifying that written informed consent was obtained before each subject's participation in the study.
- d. Verifying that the investigator is enrolling only eligible subjects.
- e. Reporting the subject recruitment rate.
- f. Verifying that source data/documents and other study records are accurate, complete, kept up to date, and maintained.
- g. Verifying that the investigator provides all the required reports, notifications, applications, and submissions, and that these documents are accurate, complete, timely, legible, dated and identify the study.
- h. Checking the accuracy and completeness of the CRF entries, source data/documents, and other study related records against each other.
- i. Informing the investigator of any CRF entry error, omission, or illegibility. The monitor should ensure that appropriate corrections, additions, or deletions are made, dated, explained, and initialed by the investigator or by a member of the study staff who is authorized to initial CRF changes for the investigator. This authorization should be documented.
- j. Determining whether all adverse events (AE's) are appropriately reported within the time periods required by GCP, the protocol, the IRB/IEC, the applicable regulatory requirement(s).
- k. Determining whether the investigator is maintaining the essential documents.
- l. Communicating deviations from the protocol, SOP's, GCP, and the applicable regulatory requirements to the investigator and taking appropriate action designed to prevent recurrence of the detected deviations.
- m. Follow the University SOP's, GCP, and the applicable regulatory requirements.

Study Monitoring

The study Principal Investigator and research staff will prepare a case record form (CRF) that is designed to reduce coding errors and promote data quality. Each page of the CRF will contain a header that includes the title of the protocol, the protocol number, the subject randomization number, subject screening number, and visit number. The technicians are responsible for data entry. The research charts will be maintained separately from the CRF and will contain subject information that is not entered in the study CRF database.

Regulatory Binder: A detailed Regulatory Binder will be assembled by the research team. Any changes to procedures are documented in this section. This binder is the backbone of quality assurance. We use this binder to train any new study personnel and for reference so that our policies and procedures are standard throughout all phases of the protocol. The 'Measures' section of the binder addresses, specifically all forms and instruments that comprise the CRF. A Table of Contents has been prepared that contains all the forms used in the study.

The study manual will include

- study protocol research team names, titles, roles and responsibilities, work and home phone numbers
- purpose of study, study intent and rationale
- all study procedures for each team member (PIs, technicians, study coordinator, pharmacists, nurses, physicians, etc.)
- recruitment and S screening procedures
- intake procedures
- study phase procedures
- completion/discontinuation procedures

Data Collection Training

The CSA provides comprehensive data collection training for all research technicians (RTs). RTs receive training on how to proceed with problematic Subjects. RTs are extensively trained on all MRI procedures. RTs are trained to follow the general data collection guidelines listed below.

- RTs should be present when subject is completing instruments.
- Research interviews and evaluations should be administered in a private, quiet office or area.
- Instruments are introduced and explained the same way each time to each subject.
- Order of research assessments should be maintained, as much as possible.
- Order of specimens obtained should be maintained as much as possible.
- RTs should show an interested, polite, appropriate, and helpful demeanor.

Quality assurance (QA) procedures

Changes to the CRF and the study database are strictly monitored. After a single line is drawn through the corrected data point, the RT documents the change by placing his or her initials and the date of the change adjacent to the correction. Typical QA responsibilities of the RT include:

- Checking all data during or immediately after study visits.
- Checking charts at predetermined points during the study (initials and date of checker are required on each form checked).
- Performing the initial data check after a few charts have been entered.
- Performing a 10% data check when all data have been entered.

Typical responsibilities of the PI include:

- Monitoring and reporting on RT interviewing and data collection proficiency at subject study visits.
- Checking charts at predetermined points during the study (initials and date of PI are required on each form checked).
- Supervising study database checks.
- When databases, in Filemaker Pro or other applications, are developed by the research staff, only the data checked by the RT are entered. Data sets are double checked in pairs by technicians. The PI supervises any corrections to the data set and reviews the completed database before the information is used in any reports or analyses.
- The PI holds meetings with the RTs to report and review the project and data entry status.
- PI reviews lab results and screening information (inclusion/exclusion checklist) for potential subjects.
- PI reviews adverse events on at least a weekly basis

Study Logs and Reports

Study logs are routinely maintained in order to keep computerized back up records of subjects identifying and socio-demographic characteristics and experimental group status. The study subject log usually includes subjects' initials, study number, CRF number, date of birth, race, medication start dates, subject status (active, drop-out, completer, follow-up) and relevant dates and comments.

Data Storage on Site

The CRFs and research charts are stored in file rooms specifically designed for data storage. All study data are housed in locked file cabinets. Only designated members of the research team have access to the file cabinets containing research data. Data are kept on site for not less than three years after the subject has completed the final assessment. Data are then eligible for archiving.

9. APPENDIX 1: (Sub-study) Baclofen effects on brain and behavior in treatment-seeking cigarette smokers who drink heavily

